In summary, there is a great-unmet need for non-invasive treatments for chronic knee pain due to OA. In this proposal, we will test whether tDCS applied in conjunction with TUS is effective in treating chronic knee pain from OA.

Sponsors

This study is to be funded by the National Institutes of Health (Highland Instruments SBIR). Highland Instruments is a company focused on developing neurostimulation technologies for treatment of neural pathologies.

II. SPECIFIC AIMS

In this study, we aim to assess the effects of tDCS in combination with TUS for the treatment of pain and functional limitations in subjects with OA of the knee. We will explore *Aim 1 Sub-aims 1.1- 1.4* with a parallel design (active tDCS+ active TUS (n=32), and sham tDCS+sham TUS (n=32)). The specific aims of this experiment are as follows:

Aim 1: Assess the preliminary therapeutic effects of tDCS in conjunction with TUS in chronic OA knee pain.

Sub Aim 1.1: Safety of tDCS+TUS in subjects with OA of the knee.

We hypothesize that tDCS in conjunction with TUS can be applied safely in OA subjects. To test this we will implement a comprehensive battery of safety and neurological tests in OA subjects following fixed doses of tDCS in conjunction with TUS provided over [REDACTED] [REDACTED] for 10 days, 20 minutes/day. These assessments include EEG recordings, Visual Analog Mood Scale (VAMS), Mini Mental Status Exam (MMSE), 4-Choice Reaction Time, adverse events (AE) questionnaire and Neurological and physical examinations. We will compare active tDCS+ active TUS (n=32), and sham tDCS+sham TUS (n=32), inactive transducers. Follow-up evaluations will continue, while no further treatment is given, for 8 weeks (at 1, 2, 4, and 8 weeks) after the last stimulation.

Sub Aim 1.2 Effects of tDCS+TUS in pain perception in subjects with OA of the knee.

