- Review inclusion and exclusion criteria.
- Obtain a signed and dated consent form.
- Conduct a Demographics Survey, Brief Medical History and the Beck Depression Inventory.
- Urine pregnancy exam (if applicable).

Confirmation of Osteoarthritis

Prior to the screening visit the subject will be asked if they can bring a document from their physician confirming the diagnosis of osteoarthritis of the knee. If the subject does not have it upon consenting, the subject will be asked to sign a medical release form allowing us to retrieve this document. If the subject is unable to obtain the medical record, a diagnosis by a study staff licensed physician will be accepted. This requirement has been outlined in the consent form. The baseline visit will only occur once confirmation of this diagnosis has been received.

Visit 2

Baseline Visit – (Approx Time: 2 hours)

This visit might be completed on the same day as the screening visit if time allows and the subject agrees.

Baseline assessments:

- Single Leg Standing Balance Test
- Step Test
- Functional Reach Test
- Timed Up and Go Test
- Knee Proprioceptive Test
- Knee Extensor/Flexor Force Test
- Knee Range of Motion (ROM)
- Visual Analogue Scale (VAS) for Pain

- Pain/Medication Diary
- Von-Frey Assessment
- Pain Pressure Test (PPT) with algometer
- Descending Noxious Inhibitory Control (DNIC)
- Western Ontario and McMaster Universities Osteoarthritis Index (WOMAC)
- Medical Outcomes Study 36-Item Short Form (SF-36)
- Visual Analog Mood Scale (VAMS)
- EEG recording
- Mini Mental Status Exam (MMSE)
- 4-Choice Reaction Time
- Neurological and Physical Exam

Visit 3

Re-screening procedure-(Approx Time: 5 minutes)

Prior to performing any assessments for visit 3, the subject will be re-screened to determine if they comply with the following inclusion and exclusion criteria: “*Pain of at least 3 on a 0-10 VAS scale on average over the week prior to the first stimulation session*”. If the subject does not report a VAS of at least 3 on a 0-10 VAS scale on average over the week prior to the stimulation session they will be screened-out of the trial and provided with the reason. If the subject does report a VAS of at least 3 on a 0-10 VAS scale on average over the week prior to the stimulation session, then they will continue with the remainder of the study visits.

1st Stimulation Visit – (Approx Time: 3.0 hours)

This study will be scheduled ~1 week after the baseline measurements were done.

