There will be 10 stimulation visits to be completed over 2 consecutive weeks (ideally Monday to Friday of each week). The subject will receive either 20 minutes of active tDCS in conjunction with active TUS, or sham tDCS in conjunction with sham TUS per day for the course of their stimulation visits.

Randomization:

Once eligibility and consent have been approved and completed, after all baseline evaluations and immediately before the first stimulation session, stratified blocked randomization will occur using the randomized list generated by an automatic web-based randomization program (www.randomization.com). A staff member who is not involved in any of the study procedures will be responsible for creating the randomization list and monitoring it during the study. Randomization will be stratified by baseline pain, using the median of Phase I as a cutoff (VAS of 7). Subjects will be randomly assigned to treatment or placebo groups in a 1:1 allocation ratio. We will use permuted blocks of variable sizes (4, 6, and 8) in a random manner to minimize the risk of study staff guessing at the next allocation. Randomization order will be kept in sealed envelopes.

Blinding:

All subjects and investigators will be blinded to the group assignment except for the co-investigators providing stimulation and staff involved in the randomization process (the latter would otherwise not be involved in study procedures). Only the staff involved in the randomization will be authorized to break the blind if there is a clinical need as requested by the PI, clinical care providers, Medical Monitor, or IMC. The patients will remain blinded until they have completed all visits (whether they complete all 16 visits or drop out early), or in the case of an adverse event necessitating un-blinding.

If the subject receives a sham stimulation, he/she may re-enroll into an open label portion of the study, where he/she will receive 10 days of active tDCS/TUS. Un-blinded co-investigators (e.g., who provided stimulation) will coordinate with subjects electing to enter into the open label phase, which will be conducted by the un-blinded study staff. The open-label study will be conducted without informing the blinded assessors of the patient enrollment. In the open label phase, we will complete the VAS assessments on Day 5 and Day 10 of stimulation. This collected data will not be analyzed with the main data collected in the study. This data will be used for exploratory analyses only.

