Before stimulation, the subject will complete a series of assessments:

- Single Leg Standing Balance Test
- Step Test
- Functional Reach Test
- Timed Up and Go Test
- Knee Proprioceptive Test
- Knee Extensor/Flexor Force Test
- Knee Range of Motion (ROM)
- Visual Analog Scale (VAS) for Pain
- Pain/Medication Diary will be given to the subject
- Von-Frey Assessment
- Pain Pressure Test (PPT) with algometer
- Descending Noxious Inhibitory Control (DNIC)
- Visual Analog Mood Scale (VAMS)
- Neurological and Physical Exam

After stimulation subjects will complete the following assessments:

- Visual Analog Scale (VAS) for Pain
- Von-Frey Assessment
- Pain Pressure Test (PPT) with algometer
- Visual Analog Mood Scale (VAMS)
- Descending Noxious Inhibitory Control (DNIC)
- Mini Mental Status Exam (MMSE)
- 4-Choice Reaction Time
- Adverse Events Questionnaire (AEs)

- EEG recording

Visits 4 – 6

Stimulation visits – (Approx Time: ¾ hour)

During the next 3 stimulation sessions – the subject will receive either 20 minutes of active tDCS in conjunction with active TUS, or sham tDCS in conjunction with sham TUS.

Pre-stimulation: immediately before stimulation, subjects will be asked to complete the following:

- Visual Analog Scale (VAS) for pain

After stimulation, the subject will complete a series of assessments:

- Visual Analog Scale (VAS) for Pain
- Visual Analog Mood Scale (VAMS)
- Mini Mental Status Exam (MMSE)
- 4-Choice Reaction Time
- Adverse Events Questionnaire (AEs)

Visit 7

5th Day of stimulation visits – (Approx Time: 2 ¼ hours)

Pre-stimulation: immediately before stimulation, subjects will be asked to complete the following:

- Visual Analog Scale (VAS) for pain

After stimulation subjects will complete the following assessments:

- Single Leg Standing Balance Test
- Step Test
- Functional Reach Test
- Timed Up and Go Test
- Knee Proprioceptive Test
- Knee Extensor/Flexor Force Test
- Knee Range of Motion (ROM)
- Visual Analog Scale (VAS) for Pain
- Pain/Medication Diary
- Von-Frey Assessment
- Pain Pressure Test (PPT) with algometer
- Descending Noxious Inhibitory Control (DNIC)
- Western Ontario and McMaster Universities Osteoarthritis Index (WOMAC)
- Visual Analog Mood Scale (VAMS)
- EEG recording
- Mini Mental Status Exam (MMSE)
- 4-Choice Reaction Time
- Adverse Events Questionnaire (AEs)

- Neurological and Physical Exam

Visits 8 – 11

6-9th Day of Stimulation visits – (Approx Time: ¾ hour)

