Pre-stimulation: immediately before stimulation, subjects will be asked to complete the following:

- Visual Analog Scale (VAS) for pain

After stimulation, the subject will complete a series of assessments:

- Visual Analog Scale (VAS) for Pain
- Visual Analog Mood Scale (VAMS)
- Mini Mental Status Exam (MMSE)
- 4-Choice Reaction Time
- Adverse Events Questionnaire (AEs)

Visit 12

10th Day of stimulation visits – (Approx Time: 2 ¼ hours)

Pre-stimulation: immediately before stimulation, subjects will be asked to complete the following:

- Visual Analog Scale (VAS) for pain

After stimulation subjects will complete the following assessments:

- Single Leg Standing Balance Test
- Step Test
- Functional Reach Test
- Timed Up and Go Test
- Knee Proprioceptive Test
- Knee Extensor/Flexor Force Test
- Knee Range of Motion (ROM)
- Visual Analog Scale (VAS) for Pain
- Pain/Medication Diary
- Von-Frey Assessment
- Pain Pressure Test (PPT) with algometer
- Descending Noxious Inhibitory Control (DNIC)
- Western Ontario and McMaster Universities Osteoarthritis Index (WOMAC)
- Medical Outcomes Study 36-Item Short Form (SF-36)
- Visual Analog Mood Scale (VAMS)
- EEG recording
- Mini Mental Status Exam (MMSE)
- 4-Choice Reaction Time
- Adverse Events Questionnaire (AEs)

- Neurological and Physical Exam

[figure not shown]
Visit 13, 14, 15, and 16

Follow-Up Visit – 1 week, 2 weeks, 4 weeks, and 8 weeks post-stimulation – (Approx Time: 2 hours)

These visits will be scheduled ~1, 2, 4, and 8 weeks after the last stimulation session and the following assessments will be performed:

- Single Leg Standing Balance Test
- Step Test
- Functional Reach Test
- Timed Up and Go Test
- Knee Proprioceptive Test
- Knee Extensor/Flexor Force Test
- Knee Range of Motion (ROM)
- Visual Analog Scale (VAS) for Pain
- Pain/Medication Diary
- Von-Frey Assessment
- Pain Pressure Test (PPT) with algometer
- Descending Noxious Inhibitory Control (DNIC)
- Western Ontario and McMaster Universities Osteoarthritis Index (WOMAC)
- Medical Outcomes Study 36-Item Short Form (SF-36)
- Visual Analog Mood Scale (VAMS)
- EEG recording
- Mini Mental Status Exam (MMSE)
- 4-Choice Reaction Time
- Adverse Events Questionnaire (AEs)
- Neurological and Physical Exam

Stimulation protocol: Subjects will be randomized to undergo one of two different treatment conditions: 10 sessions of sham tDCS/TUS, or 10 sessions of active anodal tDCS/TUS (32 subjects per study arm).

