An FDA approved assist device (Highland Instruments, Cambridge, MA) that can assist the stimulation provider in the synchronous application of TUS

and cranial electrical stimulation devices will be available if required (e.g., for operator fatigue the device can assist the operator in holding the TUS probe relative to the tDCS electrodes).

For sham tDCS/TUS, we will follow the exact procedure as above but use an inactive ultrasound transducer (i.e., the device will remain off during stimulation). For the sham condition, we will follow the exact procedure as above, however tDCS current will be applied for less than 30 seconds so that the sham subjects experience the same sensation of the device turning on as active subjects (the 'turning off' of the device is not perceived due to sensitization). It should be noted that less than 3 minutes of tDCS induces no lasting effects on cortical excitability [39]) and also using 30 seconds of sham is a reliable method of blinding, as shown by a randomized controlled study [69].

[REDACTED] Furthermore during the sham, the TUS will not be active during stimulation.

The schedule for the subjects can be seen in table 1, which illustrates the procedures that will be performed at each visit:

[REDACTED]

[REDACTED]

DESCRIPTION OF ASSESSMENTS:

A rater blind to the treatment arm will administer the following tests (also used in our previous study [70]):

Visual Analogue Scale (VAS) for Pain: The VAS is a common assessment used which asks subjects to self-reportedly measure their pain on a visual scale (i.e., unbearable to none). This will help us to monitor changes in subjects' pain levels when they come in for sessions.

Pain/Medication Diary: To help monitor pain levels, as well as safety, subjects will keep a diary listing their daily medications and pain levels when not at the laboratory.

Mechanical Detection Threshold (von-Frey MDT): This technique is adapted to evaluate light touch in small cutaneous regions [71]. The most used procedure is with the Von Frey monofilament (0.008g to 300g) via the method of limits. The examiner makes use of an ascending standardized sequence of varying stimulus intensities. In the case of ramping the stimulus up, the individual is asked to report when the sensation is first detected

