Visual Analog Mood Scale (VAMS): This is a self-assessment scale in which subjects rate their own emotions, including anxiety, depression, stress, and sleepiness along a 100 mm line.

Mini Mental Status Exam (MMSE): This is a sensitive, valid and reliable 30-point questionnaire that is used extensively in clinical and research settings to measure cognitive impairment. This instrument will be used as a brief screening of cognitive abilities. The MMSE will be administered at the baseline evaluation and every subsequent visit.

4-Choice Reaction Time: Patients will be seated in front of a computer screen placed at eye level. One of four possible circles, each 4 cm in diameter, will be presented horizontally spaced on the screen and aligned above the appropriate response keys. The stimuli will be generated and response times recorded using Superlab pro v2.0 software (Cedrus Corporation, San Pedro, Ca). The patients have to push the key aligned with the circle that appeared using only the index finger of the dominant hand. The circle will not disappear until the correct button is pushed. The time between the appearance of the circle and the push of the correct response key will be defined as the choice reaction time. The 4-choice reaction time will be administered at the baseline evaluation and every subsequent visit.

Adverse Effects Questionnaire: At each session after stimulation begins, subjects will complete a questionnaire to evaluate potential adverse effects of stimulation (headache, neck pain, mood alterations, and seizures) on a 5-point scale. The scale will also be administered at the follow-up. The subjects will be asked whether they have experienced any side effects in an open-ended manner and they will then be specifically asked about headache, neck pain, scalp pain, scalp burns, tingling, skin redness, sleepiness, trouble concentrating, and acute mood change. If any side effects are reported, the degree of relatedness to the intervention will be assessed.

We will be investigating adverse effects using open-ended questions. An AE can be any unfavorable and unintended sign, symptom, or disease temporally associated with the use of a treatment, whether or not considered related to the product.

Examples of AEs are as follows:

- Subjective symptoms offered by or elicited from the subject
- Objective signs observed by the Investigator or other study personnel

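### The adverse-effects questionnaire is never scheduled before first exposure in the visible plan, so headache, neck pain and scalp pain have no pre-dose score on it

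*Combined protocol and SAP*

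**What the plan says.** Safety is the first sub-aim. Section II, Sub Aim 1.1 states "We hypothesize that tDCS in conjunction with TUS can be applied safely in OA subjects" and names the adverse-events questionnaire among the safety assessments.

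Section VI, Description of Assessments, sets the timing: "At each session after stimulation begins, subjects will complete a questionnaire to evaluate potential adverse effects of stimulation". The form uses a 5-point scale and is repeated at follow-up. It has an open question followed by nine prompts: headache, neck pain, scalp pain, scalp burns, tingling, skin redness, sleepiness, trouble concentrating and acute mood change. Relatedness is judged for any side effect reported. The text on adverse events that follows also counts a worsening or more frequent recurrence of an existing condition, and asks about duration and causality.

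Before the first dose, the visible plan provides:

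- **Screening (Visit 1):** "Conduct a Demographics Survey, Brief Medical History and the Beck Depression Inventory".
- **Baseline (Visit 2):** 19 assessments, including the mood scale (VAMS), MMSE, 4-choice reaction time, diary, and neurological and physical exam. The adverse-effects form is not among them.
- **Visit 3:** under "Before stimulation, the subject will complete a series of assessments", 14 items, again including VAMS and the exam, without the form. It first appears in that visit's after-stimulation list.

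Table 1, which shows the procedures by visit, is redacted.

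**The concern.** Relatedness and worsening are judgements about change, and change needs a prior state. The eligibility criteria do not exclude people with headache or neck pain, so some subjects may arrive at Visit 3 with one of these symptoms. The same visit puts balance, muscle-force, pressure-pain and cold-water testing ahead of stimulation, so a symptom could also begin that day before any current is applied. A subject who reports a headache on the first form, after dose 1, gives one score with nothing on the same scale to set it against. Whether it is new, worse or old then rests on recall.

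The stake is the quality of individual attribution under a named safety aim. In addition, symptoms unrelated to stimulation enter both arms' scores and counts as background noise.

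**Working it through.** The plan gives no figure to reproduce. The check is a count over the visible visit lists, followed by a sizing under a stated assumption.

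**Step 1: where the form appears (Section VI, visit lists).**

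| Time | Administrations |
|---|---|
| Screening, Visit 2, Visit 3 before stimulation | 0 |
| After doses 1-10 (Visits 3-12) | 10 |
| Follow-up (Visits 13-16) | 4 |
| Total | 14, all after first exposure |

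The timing sentence alone could mean every session once the treatment phase has started. The lists settle it: at each stimulation visit the form is an after-stimulation item. By contrast, the descriptions of the MMSE and 4-choice reaction time, in the same part of the protocol, explicitly include baseline.

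**Step 2: which prompts lack a reference.**

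| Prompts | Number | Pre-exposure reference |
|---|---|---|
| Headache, neck pain, scalp pain | 3 | No score described |
| Scalp burns, tingling, skin redness | 3 | Local reactions, expected near zero before exposure |
| Sleepiness, mood change | 2 | VAMS at Visits 2 and 3 |
| Trouble concentrating | 1 | Partly MMSE and reaction time at Visit 2 |
| Total | 9 | |

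The main gap is therefore 3 of 9.

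**Step 3: partial sources for those three.** The medical history is brief and taken at screening. The exam is done at Visit 2 and before dose 1, but no symptom score is described for it. The diary is described as recording medications and pain levels. It is listed at Visit 2 and noted as handed out at Visit 3, so how many pre-exposure days it covers is unclear.

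**Step 4: size.** Let p be the proportion of subjects with at least one of the three symptoms just before dose 1. The documents give no p, so 5% to 20% is assumed. Expected number per arm = 32p, and in all = 64p. If subjects are independent, the standard deviation of the chance difference in counts between arms is √(2 × 32 × p(1 − p)).

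| p | Per arm | Both arms | SD of difference between arms |
|---|---|---|---|
| 5% | 32 × 0.05 = 1.6 | 64 × 0.05 = 3.2 | √(64 × 0.0475) = √3.04 = 1.7 |
| 10% | 3.2 | 6.4 | √(64 × 0.09) = √5.76 = 2.4 |
| 20% | 6.4 | 12.8 | √(64 × 0.16) = √10.24 = 3.2 |

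The expected difference between arms is zero at every p, so this is noise and not bias. The last column shows how much pre-existing symptoms alone could move a between-arm count if they persist to the post-dose form.

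**Step 5: effect on the planned analysis.** Section VII compares adverse effects between arms, with Fisher's exact test for categorical items and the same methods as for efficacy for continuous ones. A pre-dose score could enter the continuous models as a covariate. The gain depends on the correlation between pre- and post-dose scores, which is not given, so its size is unknown.

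**The case against.** The strongest reply is that no planned comparison is harmed. Safety is compared between randomised arms, and pre-existing symptoms fall on both alike. That stands. A reader might infer that the adverse-effect comparison is biased, and the documents do not support that.

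Second, existing capture is real. The diary is kept partly for safety, adverse events include symptoms that subjects volunteer, and duration and causality are already investigated. The content of the exam rests on a cited reference that is not available here, so it may record current headache. This narrows the gap but does not supply a score on the same form.

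Third, Table 1 is hidden and could show a baseline administration. That also stands as a condition. Nothing in the visible lists or the questionnaire description suggests one.

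A stronger reading is also tempting. At Visits 4-12, under "Pre-stimulation: immediately before stimulation, subjects will be asked to complete the following", the pain VAS is the only item, so a reader might infer that no side-effect question precedes doses 2-10. That is not so: the forms completed after doses 1-9 each precede the next dose. What is not listed is a same-day question before dosing. Even that cannot be asserted as missing, because the session procedure is redacted: the sham description opens "For sham tDCS/TUS, we will follow the exact procedure as above but use an inactive ultrasound transducer", and the procedure it points to cannot be seen. Staff also meet the subject just before each dose, so a delayed reaction could be mentioned then.

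**Conclusion.** The point holds for the visible text. All 14 listed administrations of the form follow first exposure, and 3 of its 9 prompts have no pre-exposure score. This weakens individual judgements of relatedness and of new versus worsened symptoms, and adds background noise to the adverse-effect comparison. It does not threaten the validity of the trial's conclusions. The improvement is worth making because it is cheap, not because a demonstrated error needs repair.

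The 1.6 to 6.4 subjects per arm rest wholly on the assumed 5% to 20%. They count subjects without a reference score, not misclassified events. The finding also assumes that the redacted Table 1 shows no baseline administration; if it does, the point is answered.

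**What to change.** First check Table 1. If it shows no pre-exposure administration:

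1. Add the existing questionnaire once at Visit 3, worded as current symptoms, as the last pre-stimulation item, after the VAS and sensory tests. The blinded rater who gives the other assessments can give it.
2. State in the questionnaire description that this score is the reference for classing a symptom as new or worsened and for judging relatedness.
3. In Section VII, use it as a covariate for the continuous adverse-effect items. For the categorical items, which go to Fisher's exact test, use it to define new-or-worsened events.

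**Cost.** One form for each of 64 subjects. At an assumed 2 to 3 minutes each, 64 × 2 = 128 minutes (2.1 hours) to 64 × 3 = 192 minutes (3.2 hours) over the trial, plus small edits to the visit list, the form's wording and Section VII. The form may slightly prime symptom awareness before the Visit 3 post-stimulation VAS. This should be similar in both arms, because the form comes before any stimulation. From Visit 4 on, subjects will have met the form under the current plan anyway.

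Separately, ask the sponsor whether the redacted session procedure includes a same-day side-effect question before dosing at Visits 4-12. Put this as a question only. A formal proceed-or-hold step is not recommended: the documents give no basis for hold criteria, it would take investigator time, and holds could cause missed doses in the two-week course, unevenly by arm if delayed reactions were commoner on active treatment.
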